## 12 EFFICACY ANALYSIS

---

### 12.1 Primary Efficacy Endpoint

The Eczema Area and Severity Index (EASI) is a static assessment to measure the severity and extent of atopic dermatitis. EASI combines the assessment of the severity of lesions and the area affected into a single score in the range 0 (no disease) to 72 (maximal disease).

The body is divided into four sections (head (h) (10% of a person's skin); arms (a) (20%); trunk (t) (30%); legs (l) (40%)). Each of these areas is scored by itself, and then the four scores are combined into the final EASI.

 INNOVADERM RESEARCH INC.	STATISTICAL ANALYSIS PLAN, Final V1.0Final 1.0
Protocol Number: AQR-151-212	Sponsor: Arcutis, Inc.

For each section, the percent of area (A) of skin involved is estimated and then transformed into a grade from 0 to 6 (A):

0. 0% of involved area
1. < 10% of involved area
2. 10–<30% of involved area
3. 30–<50% of involved area
4. 50–<70% of involved area
5. 70–<90% of involved area
6. 90–100% of involved area

EASI is evaluated for the entire body except the scalp, palms, and soles.

Within each area, the severity is estimated by four clinical signs: Redness (erythema, inflammation), Thickness (induration, papulation, swelling – acute eczema), Scratching (excoriation), and Lichenification (lined skin, furrowing, prurigo nodules – chronic eczema). Severity parameters are measured on a scale of 0 to 3, from none to severe.

To calculate the EASI, the sum of the severity rating for the four clinical signs are multiplied with the numerical value of the area affected and with the various percentages of the four body areas (see [Appendix 3](#)). The score will be set to missing in case of at least one missing value.

Descriptive statistics on EASI total score will be presented by visit for each treatment group. Change from baseline and percentage change from baseline will be also summarized.

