9.6 Selection of Study Population

9.6.1 Inclusion Criteria

Subjects must fulfill all of the following inclusion criteria to be eligible for participation in the study:

1. Participants legally competent to sign and give informed consent or, in the case of adolescents, assent with consent of a parent(s) or legal guardian, as required by local laws.
2. Males and females ages 12 years and older (inclusive) at the time of consent.
3. Clinical diagnosis of active atopic dermatitis according to the criteria of [Hanifin and Rajka \(1980\)](#). Subjects must have at least 3 of the 4 basic features (1. Pruritus; 2. Typical morphology and distribution [flexural lichenification in adults and facial and extensor eruptions in infants and children]; 3. Chronic or chronically relapsing dermatitis; or 4. Personal or family history of atopy), in addition to at least 3 minor criteria.
4. History of AD for at least 4 months as determined by the Investigator through subject interview. Stable disease for the past 3 weeks with no significant flares in atopic dermatitis before screening.
5. BSA involvement of at least 1.5% (excluding the scalp, palms, and soles) but no more than 35%, at Baseline (Visit 2).
6. vIGA-AD score of ‘mild’ (‘2’) or ‘moderate (‘3’) at Baseline (Visit 2). vIGA-AD is evaluated for the entire body except the scalp, palms, and soles.
7. Subject has an EASI score of ≥ 5 at Baseline (Visit 2). EASI is evaluated for the entire body except the scalp, palms, and soles.
8. Females of childbearing potential (FOCBP) must have a negative serum pregnancy test at Screening (Visit 1) and a negative urine pregnancy test at Baseline (Visit 2). In addition, sexually active FOCBP must agree to use at least one form of highly effective contraception throughout the duration of the trial and for one week after application of the last dose. Highly effective forms of contraception include: oral/implant/injectable/transdermal contraceptives, intrauterine device, and partner’s vasectomy. If barrier methods are used (e.g., condom with spermicide, diaphragm with spermicide), then 2 forms of conception are required in association with spermicide. The use of abstinence as a contraceptive measure is acceptable as long as this is a consistent part of a lifestyle choice and an acceptable backup method has been identified if the subject becomes sexually active.

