### 6.2 Handling of Dropouts or Missing data

See [Appendix 2](#) for handling of completely or partially missing dates for prior and concomitant medications and adverse events.

The primary method of handling of missing data will be the MMRM method without explicit imputations for missing data. A sensitivity analysis will be carried out on the primary endpoint using the last observation carried forward (LOCF) as an imputation for missing data. Only post-baseline values will be carried forward.

For secondary endpoints involving proportions, missing data at any post-baseline assessment will be imputed using LOCF and they will then be determined as a responder or non-responder based on the LOCF value.

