## Appendix 3 EASI Scoring Tool

### **Eczema Area and Severity Index (EASI) case report form - age≥8 years**

**Area of Involvement:** Each body region has potentially 100% involvement. Score 0 to 6 based on the following table:

% involvement	0	1-9%	10 - <30%	30 - <50%	50 - <70%	70 - <90%	90 - 100%
Region score	0	1	2	3	4	5	6

**Severity of Signs:** Grade the severity of each sign on a scale of 0 to 3:

0	None
1	Mild
2	Moderate
3	Severe

- ✓ Take an average of the severity across the involved area.
- ✓ Half points (1.5 and 2.5) may be used. 0.5 is not permitted – if a sign is present it should be at least mild (1)

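### The missing-item rule for EASI in SAP 12.1 makes no exception for a region with area grade 0, so an exactly known total is discarded if a sign item there stays blank

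*SAP*

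**What the plan says.** **Score.** SAP 12.1 describes the calculation in these words: "the sum of the severity rating for the four clinical signs are multiplied with the numerical value of the area affected", and then with the region weight (head 0.1, arms 0.2, trunk 0.3, legs 0.4). Area grade 0 stands for "0% of involved area". On the signs it says: "Severity parameters are measured on a scale of 0 to 3, from none to severe".

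**Missing items.** The same section adds: "The score will be set to missing in case of at least one missing value". Neither SAP 12.1 nor SAP Appendix 3 qualifies this for an uninvolved region.

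**Instructions to the rater.** The scoring tool (SAP Appendix 3, Protocol Appendix 4) says: "Take an average of the severity across the involved area". It also says that a sign that is present must be graded at least 1. Footnote c of the schedule (Protocol Section 5, SAP Table 1) has the four signs graded from 0 for absent to 3 for severe in the four regions. None of these places says what to enter when involvement is 0%.

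**What happens to a missing total.** SAP 6.2 says: "The primary method of handling of missing data will be the MMRM method without explicit imputations for missing data". For secondary endpoints that are proportions, "missing data at any post-baseline assessment will be imputed using LOCF". LOCF is also the sensitivity analysis for the primary endpoint (SAP 6.2 and 12.1). Under SAP 5.2, baseline is the last non-missing value up to the first dose date.

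**The concern.** A rule that voids the total when any item is blank suits a sum, where each item carries its own information. EASI is a sum of products, and an area grade of 0 fixes its region at 0. The same sentence appears in SAP 13.6 for the PHQ-8, a plain sum, which suggests a general rule that was not adapted to EASI.

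A blank is plausible here. The tool asks for severity averaged over the involved area, and a clear region has none. Some raters would enter 0, and some might skip the row.

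If that happens, three things are at stake:

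- **Primary analysis.** The Week 4 value drops out of the MMRM. If blanks follow clearance, missingness depends on the current, unrecorded total, which a likelihood analysis without imputation does not correct. The LOCF sensitivity analysis inherits the same false gap.
- **Responder endpoints.** EASI50, 75, 90 and 100 take an earlier value, usually worse in an improving subject.
- **Baseline.** A subject with an uninvolved region could lose the Baseline total and fall back to Screening, up to 4 weeks earlier. That value may precede the 1-week washout of topical treatments in Protocol Table 1.

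**Working it through.** **1. The plan's own figures.** The maximum region score is 12 x 6 x weight. The weights sum to 0.1 + 0.3 + 0.2 + 0.4 = 1, so the maximum total is 72, as SAP 12.1 states. The sample size also reproduces and does not depend on this point: with difference 35%, SD 40%, a two-sample t-test and two-sided 0.025 (Bonferroni, two comparisons), power is 79.8% at 26 per arm and 81.5% at 27.

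**2. A region with area grade 0.** Region score = S x 0 x weight = 0 for every sign sum S from 0 to 12 and for all four weights. The signs are not needed to know the region score.

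**3. One subject (constructed values).** Baseline EASI 8 and Week 2 EASI 3.0. At Week 4, head and trunk are clear, and arms and legs each have area grade 1 and sign sum 2.

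- Week 4 EASI = 0.2 x 1 x 2 + 0.4 x 1 x 2 = 0.4 + 0.8 = 1.2.
- Improvement = (8 - 1.2) / 8 = 85%, an EASI75 responder.
- If one sign for the head or trunk is blank, the total is missing and LOCF uses 3.0: (8 - 3.0) / 8 = 62.5%, a non-responder.

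**4. Chance of losing a known total.** Let k be the number of regions with area grade 0, and q the chance that such a region has a blank sign, independent between regions. The loss is 1 - (1 - q)^k. The documents give no q, so these values are assumptions:

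| q | k = 1 | k = 2 | k = 3 | k = 4 |
|---|---|---|---|---|
| 0% | 0% | 0% | 0% | 0% |
| 2% | 2.0% | 4.0% | 5.9% | 7.8% |
| 5% | 5.0% | 9.8% | 14.3% | 18.5% |
| 10% | 10.0% | 19.0% | 27.1% | 34.4% |
| 25% | 25.0% | 43.8% | 57.8% | 68.4% |

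**5. Direction (simulation, every input assumed except the entry limit).** Subjects had EASI of at least 5 at entry. Before that limit was applied, 40% of regions were uninvolved. By Week 4, 15% of involved regions cleared on vehicle and 35% on active. The table compares observed-case means, not a fitted MMRM. With nothing lost, the difference in change from baseline was -1.74 to -1.77 points across runs.

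| q | Difference, blanks only in newly cleared regions | Lost, vehicle / active | Difference, blanks in any region with area grade 0 | Lost, vehicle / active |
|---|---|---|---|---|
| 2% | -1.74 | 0.8% / 2.0% | -1.73 | 3.1% / 4.3% |
| 5% | -1.70 | 2.2% / 4.8% | -1.70 | 7.8% / 10.3% |
| 10% | -1.65 | 4.1% / 9.4% | -1.65 | 14.8% / 19.6% |
| 25% | -1.47 | 9.6% / 21.7% | -1.51 | 34.1% / 43.2% |

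The difference shrinks toward zero, by an amount set by q.

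**The case against.** The strongest reply is that blanks should be rare. Footnote c calls for all four signs in all four regions with a grade for absence, so a clear region has a natural entry of four zeros. Protocol 12.4 requires a 100% quality control check and edit checks for missing data, with corrections before lock, and a blank sign beside area grade 0 is easy to resolve. The electronic form, which is not in the documents, may force an entry or fill in 0. Sites must also have a working total at Baseline, because inclusion criterion 7 needs an EASI of at least 5 there. If no blank survives, nothing is lost.

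Most of this stands, and it makes the point conditional. It does not justify the rule. Footnote c has no clause for 0% involvement, the tool's averaging instruction points the other way, and a missing-item rule operates only on blanks that remain after cleaning. SAP 13.5 records that two sites misread the local tolerability form. That is a different form, but it shows that misreading occurred in this trial.

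A reader might go further and infer that known EASI values are in fact being lost selectively in subjects who cleared. The documents do not show that any sign is left blank. The rule also reaches regions that were never involved, in every arm and at every visit; with entry allowed from 1.5% BSA, these may be common.

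**Conclusion.** The gap in the rule is certain: as written, it discards a total that is exactly determined whenever a sign is blank in a region with area grade 0, and neither the MMRM nor LOCF repairs this. Whether it costs anything depends on blanks remaining at lock. To the extent that they follow clearance, the bias is toward no effect, so it would understate the drug effect.

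The size cannot be derived from the documents. Any percentage of lost EASI values is a product of assumed rates, and the tables above show only range and direction.

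A reader might also infer that a fully clear subject could never count for EASI100. That is too strong: with the signs entered as 0 the total is 0, and even with blanks LOCF would carry a complete earlier EASI of 0. What holds is that such a subject is scored from an earlier visit, which matters most for EASI90 and EASI100.

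This is a safeguard for the primary endpoint that costs almost nothing, not a demonstrated bias.

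**What to change.** Replace the missing-item sentence for EASI in SAP 12.1 with:

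> *If the area grade of a region is 0, the region score is 0 whether or not its sign items are recorded. The EASI total is set to missing only if an area grade is missing, or if a sign item is missing in a region with area grade 1 or more.*

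Apply it at all visits, including Baseline, and before database lock, since SAP 3.4.3 has the SAP finalized by then. The cost is one sentence and one line of derivation code, with no new data. If the case never arises, no result changes.

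A blinded count before lock of the EASI totals that the present rule sets to missing, split by whether the blank sign lies in a region with area grade 0 or above 0, would show whether the point has any practical size.

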### Primary Endpoint Analysis

The primary efficacy endpoint is change from baseline in EASI Total Score at Week 4.

The primary efficacy endpoint will be analyzed using a MMRM analysis on change-from-baseline EASI with subject as a random effect and vIGA-AD strata, visit, treatment group, and interaction term for treatment-by-visit as fixed effects and baseline EASI as a fixed covariate. An unstructured variance-covariance matrix will be used. The Kenward-Roger approximation will be used to estimate denominator degrees of freedom. The primary treatment comparisons will be the contrast between each dose of ARQ-151 with the Vehicle at Week 4.

### Sensitivity Analyses

The interaction term baseline value-by-treatment will also be included in a supportive statistical model.

 INNOVADERM RESEARCH INC.	STATISTICAL ANALYSIS PLAN, Final V1.0Final 1.0
Protocol Number: AQR-151-212	Sponsor: Arcutis, Inc.

Missing data is handled using MMRM without explicit imputations for missing data. To assess robustness of the primary method of analysis via MMRM, a sensitivity analyses using LOCF will be performed.

The primary efficacy analysis will be performed using the ITT population and the PP population will be used as supportive analysis.

#### Subgroup Analyses

An analysis of variance (ANCOVA) will be performed using LOCF to handle missing data, where the absolute change from baseline or the percent change from baseline in EASI score at Week 4 will be the dependent variable, the treatment group, vIGA-AD strata and age group (adolescents or adults) will be fixed effects. Treatment effect per age group and vIGA-AD strata will be presented.

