## 6.7 Examination of Subgroups

Subset analysis by age group (adolescents and adults) will be conducted for both safety and efficacy data. Subset analysis by vIGA-AD strata (“2” (mild) and “3” (moderate)) will also be conducted on the primary and secondary efficacy endpoints. Details on these analyses are described in Sections 12.1, 12.2, and 13.

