### **Secondary Endpoint Analysis**

Descriptive statistics will be presented on all secondary endpoints by visit and treatment group.

A similar analysis approach as outlined for the primary endpoint will be used for all secondary continuous efficacy endpoints. The comparisons of each dose of ARQ-151 with the vehicle will be presented.

For categorical efficacy endpoints involving proportions (e.g. achievement of a 75% or greater improvement in EASI score from baseline at each study visit), a Cochran Mantel Haenszel test (CMH) controlling for the stratification variable will be performed. The comparisons of each dose of ARQ-151 with the vehicle will be presented.

Subgroup analyses by vIGA-AD strata and age-group will be performed on all secondary endpoints.

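### The subgroup ANCOVA has main effects only, so as written it gives one dose-vehicle difference for every subgroup instead of the promised effect per age group and vIGA-AD stratum

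*SAP*

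**What the plan says.** SAP 6.7 plans subgroup work on efficacy by age and by vIGA-AD stratum: "Subset analysis by age group (adolescents and adults) will be conducted for both safety and efficacy data", and the analysis by stratum "will also be conducted on the primary and secondary efficacy endpoints". It gives no method and sends the reader on: "Details on these analyses are described in Sections 12.1, 12.2, and 13".

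SAP 12.1, Subgroup Analyses, holds the only subgroup model. "An analysis of variance (ANCOVA) will be performed using LOCF to handle missing data", with absolute or percent change in EASI at Week 4 as the outcome. Of the model terms it says that "the treatment group, vIGA-AD strata and age group (adolescents or adults) will be fixed effects". The next sentence states the output: "Treatment effect per age group and vIGA-AD strata will be presented".

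SAP 12.2 says "Subgroup analyses by vIGA-AD strata and age-group will be performed on all secondary endpoints" and names no subgroup model. SAP 13 covers safety, where no inferential statistics are planned.

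The SAP names two treatment interactions: treatment-by-visit in the primary MMRM and baseline value-by-treatment in a supportive model. Neither involves age group or vIGA-AD stratum. Protocol 11.2.1 left any further interaction terms to the SAP.

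**The concern.** The two sentences in SAP 12.1 do not fit together. A model with only main effects of treatment, stratum and age assumes that each dose has the same effect in adolescents, adults, mild and moderate subjects. It cannot then estimate how that effect differs between them.

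Two analysts could follow this SAP faithfully and produce different subgroup tables: one common effect repeated in each row, contrasts from a model with interactions that the SAP does not list, or separate fits within subgroups. Under the first, a real difference between age groups or strata is averaged away, and identical rows could be misread as evidence of a consistent effect. Adolescents and adults are both named in the study objectives, and the protocol asks for results by age group, so the table will be read.

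**Working it through.** **Plan's own figure.** The subgroup section states none. The plan's only power figure is 27 per arm for at least 80% power (SAP 5.1; Protocol 11.1.4). A two-sample t-test with difference 35, SD 40 and two-sided alpha 0.05/2 = 0.025 needs 26.13 per arm, so 27, with 81.5% power at 27. The figure reproduces, and 35 and 40 are used below as percentage points.

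**Structure of the listed model.** For arm i, stratum j and age group k:

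E[Y] = mu + treatment_i + stratum_j + age_k

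Dose minus vehicle, within any stratum j and age group k:

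(mu + treatment_dose + stratum_j + age_k) − (mu + treatment_vehicle + stratum_j + age_k) = treatment_dose − treatment_vehicle

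Neither j nor k remains. Three arms give 2 treatment parameters and so 2 differences. The promised table needs 2 doses × (2 age groups + 2 strata) = 8.

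**Check on simulated data.** One data set of 105 subjects, 35 per arm, was generated with true effects that differ by age and stratum (assumed mix: about 20% adolescent, about 70% moderate).

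- Listed model: −17.985 for 0.05% and −32.141 for 0.15%, identical in all four age-by-stratum cells.
- Listed model plus baseline EASI: −17.798 and −32.511, again identical in all four cells.
- Treatment-by-age and treatment-by-stratum terms added, 0.15%: adolescent/mild +14.7, adolescent/moderate +13.9, adult/mild −38.9, adult/moderate −39.6.
- Separate fits by age group, 0.15%: adolescents +20.2, adults −39.4.

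These values come from a single noisy draw and say nothing about the drug. They confirm the algebra and show that interaction contrasts and separate fits also differ from each other.

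**Size of the averaging, without noise.** Assume a 35-point benefit over vehicle in adults, none in adolescents, and the same adolescent share p in each of three equal arms. The listed model targets (1 − p) × 35 + p × 0:

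| p (assumed) | Listed model, both age groups | With treatment-by-age: adults / adolescents |
|---|---|---|
| 0.1 | 0.9 × 35 = 31.5 | 35 / 0 |
| 0.2 | 0.8 × 35 = 28.0 | 35 / 0 |
| 0.3 | 0.7 × 35 = 24.5 | 35 / 0 |

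**Precision of a subgroup estimate.** SD 40 and N = 30 to 35 per arm are from SAP 5.1. The 95% half-width for one dose versus vehicle in adolescents, from the interaction model, is t(0.975, 3N − 7) × 40 × √(2/(N × p)). Overall it is t(0.975, 3N − 5) × 40 × √(2/N).

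| | N = 30 | N = 35 |
|---|---|---|
| Adolescents, p = 0.1 | 65.0 | 60.0 |
| Adolescents, p = 0.2 | 45.9 | 42.4 |
| Adolescents, p = 0.3 | 37.5 | 34.6 |
| Overall | 20.5 | 19.0 |

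**The case against.** The strongest reply is that nobody would run the literal version. The term subset analysis in SAP 6.7 ordinarily means an analysis within each subset, and the required output rules out a table with the same number in every row. Listing both factors is compatible with this: in the age subsets the stratum is the adjustment factor, and in the stratum subsets age is. The factor that defines the subset is constant there and is absorbed by the intercept, so the treatment contrasts remain estimable. On that reading the promised table is produced.

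This is a plausible account of the intent, and a competent analyst might well do it. But SAP 12.1 describes one ANCOVA with both factors in it and nowhere says that it is fitted by subgroup. SAP 13, by contrast, says outright that safety results are shown separately for adults and adolescents. Interaction contrasts are an equally reasonable repair and give different estimates, so the choice should be made before unblinding.

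Three other points stand. The 35-versus-0 scenario is extreme and hypothetical. Adolescent estimates will be imprecise under any model, with half-widths of about 35 to 65 points against a design effect of 35. And SAP 12.2 does give general methods for the secondary endpoints that could be applied by subset, so its silence on a subgroup model is only missing detail. Low precision does not defend the listed model, however: a wide subgroup-specific interval shows the uncertainty, while a common estimate under a subgroup label hides it.

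**Conclusion.** The concern holds. A single fit of the model in SAP 12.1 yields 2 dose-vehicle differences where 8 are promised, and no other section supplies the missing interaction or an instruction to fit by subgroup. This is algebra and rests on no assumed figure. The 31.5, 28.0 and 24.5-point illustration and the adolescent half-widths do rest on an assumed adolescent share of 10% to 30%, equal across arms.

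The consequence is confined to descriptive subgroup reporting. The primary MMRM contrast, the Dunnett adjustment and the sample size do not change. It should still be fixed, because the plan as written cannot deliver its own stated output and the repair is cheap.

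**What to change.** In SAP 12.1, choose one of these and write it down:

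- for each subgroup factor in turn, add the treatment-by-subgroup interaction to the ANCOVA; or
- state that the ANCOVA is fitted separately within each subgroup, with the factor that defines the subgroup dropped.

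The first pools the residual variance over all subjects, which helps when a subgroup has few subjects per arm. Report the Week 4 difference and 95% CI for each dose versus vehicle within each subgroup, plus the interaction estimate if the first option is used, all labelled descriptive. In SAP 12.2, state which subgroup model applies to the continuous secondary endpoints.

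Separately, and at no cost, add baseline EASI as a covariate when absolute change is the outcome. The primary MMRM has "baseline EASI as a fixed covariate", whereas this ANCOVA lists no baseline term. The gain in precision depends on a baseline-change correlation that the documents do not give. Its absence is not the cause of the common-effect problem.

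The cost is one or two sentences in SAP 12.1 and 12.2 and a few lines of code, with no new data.

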### 6.1 Adjustments for Covariates

For the efficacy parameters analyzed using a mixed-effects model for repeated measures (MMRM), the corresponding baseline value and the stratification factor vIGA-AD score (“2” (mild) or “3” (moderate)) will be included as covariates in the statistical model.

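### The subgroup ANCOVA omits baseline EASI, which costs precision on absolute change and leaves subgroup effects open to chance imbalance within vIGA-AD strata

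*SAP*

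**What the plan says.** SAP 12.1, Subgroup Analyses, sets out one model for two outcomes: "where the absolute change from baseline or the percent change from baseline in EASI score at Week 4 will be the dependent variable". The method is introduced as follows: "An analysis of variance (ANCOVA) will be performed using LOCF to handle missing data". On the model terms, it says that "the treatment group, vIGA-AD strata and age group (adolescents or adults) will be fixed effects". The promised output is: "Treatment effect per age group and vIGA-AD strata will be presented". No continuous covariate is named.

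The primary model in the same section does include one: "interaction term for treatment-by-visit as fixed effects and baseline EASI as a fixed covariate". The general rule in SAP 6.1 opens with a restriction: "For the efficacy parameters analyzed using a mixed-effects model for repeated measures (MMRM), the corresponding baseline value" is a covariate, alongside the vIGA-AD stratum. The subgroup model is not an MMRM, so the rule does not reach it.

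**The concern.** Absolute change in EASI is bounded by where the subject starts. A subject at 20 can lose up to 20 points; a subject at 5 can lose at most 5. Protocol 9.6.1 sets an EASI floor of 5 and no EASI ceiling, with BSA allowed from 1.5% to 35%, so EASI can vary widely within a vIGA-AD grade. The two-level vIGA-AD factor therefore captures only part of baseline severity. Randomization is stratified by vIGA-AD alone, so neither age nor EASI is balanced by design among adolescents.

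Two things are at stake. Subgroup estimates on the absolute scale are less precise than they need to be. A dose-vehicle difference within a small subgroup may also partly reflect which arm happened to start with more disease. Readers will set these estimates beside the primary result to judge consistency, and the two would differ in baseline adjustment for no stated reason.

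**Working it through.** **1. The plan's own figure.** The subgroup section states no number. The SD used below comes from the sample-size section (difference 35%, SD 40%, two-sided 0.05 with Bonferroni over two doses). A two-sample t-test at 0.05/2 = 0.025 first reaches 80% power at 27 per arm (81.5%), so the stated 27 reproduces. The point does not depend on it.

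**2. Does any other section supply the term?**
- SAP 6.1 does not, as shown above.
- SAP 6.7 refers back to 12.1, 12.2 and 13 and adds no covariate.
- SAP 3.5, on changes from the protocol, does not mention it.
- The protocol promises an age subset but gives no model for it.
- SAP 12.2 may do so for percent change only; see the objection.

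**3. General size.** Let ρ be the within-group correlation between baseline EASI and the outcome (not given; assumed 0.2 to 0.8). Adding baseline multiplies the standard error by √(1 − ρ²), so the variance without baseline, divided by that with it, is 1/(1 − ρ²).

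| ρ | CI narrower by | Variance ratio |
|---|---|---|
| 0.2 | 2% | 1.04 |
| 0.3 | 5% | 1.10 |
| 0.5 | 13% | 1.33 |
| 0.7 | 29% | 1.96 |
| 0.8 | 40% | 2.78 |

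**4. Simulated size, absolute change.** Assumptions: 33 per arm; baseline EASI at least 5, mean 8 to 10, CV 0.4 to 0.6; mean change −35% on vehicle and −70% on active, applied in proportion to baseline; SD 40% (read as the SD of percent change), floored at −100%. The fitted model has treatment, vIGA-AD, age and treatment-by-age, with and without baseline. The treatment-by-age term was added because the model as listed yields only one common treatment effect. Several sets of runs gave variance ratios from 1.15 to 1.70 (for example 1.23 to 1.70 in one set and 1.15 to 1.56 in another, with a different assumed link between vIGA-AD and EASI). A ratio of 1.15 is like discarding 1 − 1/1.15 = 13% of the subgroup; 1.7 is like discarding 1 − 1/1.7 = 41%.

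**5. Simulated size, percent change.** The same scenario gave ratios of 0.97 to 1.00. Under proportional response, percent change does not depend on baseline, so there is nothing to gain and almost nothing to lose.

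**6. Weaker correlation, absolute change.** Assumptions: one stratum; baseline 5 plus a lognormal with median 4; same response model; 2,000 trials per row.

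| Log-SD | n per arm | ρ | SE without | SE with | Variance ratio |
|---|---|---|---|---|---|
| 0.3 | 8 | −0.18 | 1.650 | 1.659 | 0.99 |
| 0.3 | 15 | −0.18 | 1.210 | 1.198 | 1.02 |
| 0.5 | 8 | −0.30 | 1.849 | 1.781 | 1.08 |
| 0.5 | 15 | −0.30 | 1.376 | 1.300 | 1.12 |
| 0.7 | 8 | −0.40 | 2.173 | 1.869 | 1.35 |
| 0.7 | 15 | −0.41 | 1.567 | 1.377 | 1.30 |

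The last column is (SE without / SE with)². The gain runs from nil to a 14% smaller SE.

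**7. Chance imbalance.** The difference between two arms in mean baseline has SD √(2/n) in units of the baseline SD. The relevant SD is the one within vIGA-AD strata, because the stratum is already in the model. The probability of a difference above 0.5 SD is 43% at 5 per arm, 32% at 8, 26% at 10 and 17% at 15, against 3.6% at 35. The subgroup sizes are assumed.

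**8. What the covariate cannot cure.** At 8 per arm, the 95% half-width for one dose against vehicle is 1.07 outcome SDs (42.9/40). With ρ = 0.5 it falls to 0.94 (37.4/40). Most of the imprecision comes from subgroup size.

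**The case against.** The case for leaving the model alone has four parts.

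- **Partial adjustment exists.** vIGA-AD is a baseline-severity factor; it is in the model and it stratifies randomization. This stands: adjustment is partial, not absent.
- **Percent change gains nothing.** This stands. The precision argument applies to absolute change only.
- **SAP 12.2 may already cover percent change.** It applies a similar approach to the primary for continuous secondary endpoints, which include percent change in EASI, and calls for subgroup analyses by stratum and age on all of them. That can be read as baseline-adjusted. It does not reach absolute change at Week 4, which is the primary endpoint, and it sits awkwardly with 12.1, which puts percent change in the ANCOVA.
- **A larger gap sits in the same sentence.** No treatment-by-subgroup term is listed, so the model cannot give effects per subgroup unless it is fitted separately in each. This is true, but it is a separate flaw, and repairing it would not add baseline EASI.

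A reader might infer more: that the subgroup effects are biased, or that imbalance could shift them by an amount that can be calculated. The documents support neither. Under randomization, omitting baseline causes no systematic bias. Taking the total baseline SD (8 × 0.4 = 3.2 up to 10 × 0.6 = 6.0 points) with 5 adolescents per arm would give a baseline-difference SD of 2.0 to 3.8 points (SD × √(2/5)). That overstates the exposure, because the stratum term removes part of that spread, and the 5 per arm is itself an assumption.

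**Conclusion.** The omission is plain in the text, and no section supplies the term for absolute change. The consequence is lost precision and exposure to chance imbalance within vIGA-AD strata. The variance penalty is roughly 1.15 to 1.7 under the baseline distribution, proportional response and 40% SD assumed in step 4, and close to none if the within-stratum correlation is as low as in the first rows of step 6. The direction is secure; the size is not. Nothing in these figures supports a precision claim for percent change.

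The severity is minor to moderate. The subgroup results feed no decision rule, the Dunnett control in SAP 6.6 covers only the primary dose comparisons, and the trial is a Phase 2 proof of concept. The use of both ANCOVA and analysis of variance for the same model is compatible with a drafting slip, but the documents do not settle that.

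**What to change.** - **SAP 12.1, Subgroup Analyses:** add baseline EASI total score as a continuous covariate in the model for absolute change, as in the primary model.
- **SAP 6.1:** extend the covariate rule from MMRM analyses to the ANCOVA, so that the two sections agree.
- **Percent change:** using the same covariate is reasonable for consistency with the primary model and SAP 12.2. State that reason, and say which section governs the percent-change subgroup analysis.

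The cost is a clause in each section and one degree of freedom in each model. Baseline EASI is already required at entry and used in the primary model, so no new data are needed. The change should be made before database lock, so that the choice of covariate is not open to later argument.
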